6.11.3 Sensitivity Analysis

6.11.3.1 Pattern-Mixture Model

To assess the robustness of the results to deviations from the MAR assumption in the primary analysis, a sensitivity analysis will be conducted such that non-monotone missing data will be

imputed under a missing at random (MAR) assumption while the monotone missing data will be imputed under a missing not at random (MNAR) assumption (i.e., that missingness is also dependent on the unobserved variable values).

This analysis will therefore provide a stress test of the MAR assumption in the primary analysis and will provide a conservative estimate of the treatment effect.

The pattern-mixture modeling will be implemented by first turning the non-monotone missing data pattern into a monotone missing pattern using the Markov Chain Monte Carlo (MCMC) method in SAS' PROC MI with the IMPUTE = MONOTONE and the PRIOR = JEFFREYS options to specify a non-informative prior for the MAR imputation process. Then the MONOTONE statement along with the MNAR statement with option MODEL in SAS' PROC MI will be utilized to implement the MNAR assumptions and control-based pattern-imputation^{2,3}. The inference of this sensitivity analysis will be based on the combined estimates using the standard multiple imputation technique via Rubin's⁴ rules.

Missing data will be imputed using a pattern-mixture model approach that uses a control-based pattern imputation. With this approach, subjects who discontinued from the NYX-2925 treatment group will be assumed to follow a similar outcome trajectory as subjects from the placebo (control) group, and subjects who discontinued from placebo (control) group are modeled as compliers within their own group (MAR within control group). That is, the imputation model for the missing observations in the NYX-2925 treatment group is constructed not from the observed data in the NYX-2925 treatment group, but rather from the observed data in the placebo group. This model is also the imputation model that will be used to impute missing observations in the placebo group. The missing values for each variable will be imputed based on a model simulated from the posterior predictive distribution of the conditional regression model fitted on the imputed variable using only the observations from the placebo group. This will be implemented by utilizing the MONOTONE REG statement and MNAR statement with option MODEL of SAS' PROC MI with options nimpute=20 and seed=373613962.

The following is the sample SAS code that will be used to implement the control-based pattern mixture imputation:

```
PROC MI DATA=DATAIN OUT=DATAIN_MONO SEED=373613962 NIMPUTE=1;
  BY TREATMENT;
  VAR BASELINE NRS_Week1-NRS_Week12;
  MCMC CHAIN=MULTIPLE IMPUTE=MONOTONE PRIOR = JEFFREYS;
  RUN;
```

```

PROC MI DATA= DATAIN_MONO SEED=373613962 NIMPUTE=20
OUT=DATA_IMPUTED;
CLASS TREATMENT SITE;
MONOTONE REG(NRS_Week1-NRS_Week12);
MNAR MODEL(NRS1_Week1-NRS_Week12 /
MODELOBS=(TREATMENT='Placebo'));
VAR SITE BASELINE NRS_Week1-NRS_Week12;
RUN;

```

Once all the weekly mean NRS scores are imputed, the change from baseline at each week will be calculated and consequently will be analyzed using the same MMRM model employed in the primary analysis.

The following sample SAS code will be used:

```

PROC MIXED DATA= IMPUTED ALL;
BY IMPUTATION ; /* 20 sets of results produced */
CLASS USUBJID SITE TREATMENT WEEK;
MODEL CFB = TREATMENT WEEK SITE TREATMENT*WEEK BASELINE / DDFM=KR;
REPEATED WEEK / SUBJECT=USUBJID TYPE=UN;
* extract two-sided 95%CI of LS MEANS each treatment groups by week;
LSMEANS TREATMENT*WEEK / DIFF CL;
* extract one-sided 95%CI of LS MEANS each treatment groups by week;
LSMEANS TREATMENT*WEEK / DIFF CL ALPHA=0.10;
ODS OUTPUT LSMEANS=LSMEANS DIFFS=DIFFS;
RUN;

```

Then the results are to be summarized using PROC MIANALYZE, where the treatment group LS means and their differences between treatments will be combined across all 20 imputed datasets:

```

PROC SORT DATA= LSMEANS; BY _IMPUTATION_ TREATMENT WEEK; RUN;
PROC MIANALYZE PARMs= LSMEANS;
MODELEFFECTS ESTIMATE;
STDERR STDERR;
ODS OUTPUT PARAMETERESTIMATES= LSMEANS_COMB;
BY TREATMENT WEEK;
RUN;
PROC SORT DATA= DIFFS; BY TREATMENT;
RUN;

```

```
PROC MIANALYZE PARMS= DIFFS (WHERE=(WEEK=_WEEK)) ;
  MODELEFFECTS ESTIMATE;
  STDERR STDERR;
  ODS OUTPUT PARAMETERESTIMATES= DIFFS_COMB;
  BY TREATMENT;
  RUN;
```

LS means, SEs, and 95% CIs for each treatment group based on the combined analysis of multiple imputed datasets will be presented for each week alongside the estimate of the treatment difference, SE, one-sided CIs and p-values.

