6.11 Efficacy Analyses

All statistical tests will be performed using a one-tailed 5% overall significance level as primary analysis. All comparisons between treatments will be reported with one-sided 95% confidence intervals (CI). All analyses will be performed independently on the treatment groups.

All statistical tests will be repeated using a two-sided 5% overall significance level, unless otherwise stated. All comparisons between treatments will be also reported with two-sided 95% CI.

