6.11.3.2 Tipping Point Analysis

If the primary efficacy analysis in Section 6.11.2 significantly favors any NYX-2925 treatment group, a tipping point sensitivity analysis⁴ for the primary efficacy endpoint will be conducted to investigate how severe the departure from the MAR assumption data must be to overturn conclusion from the primary analysis.

In this analysis, the assumption will be that that missing data in the NYX-2925 groups follows a MNAR pattern. A tipping point-based approach will be used such that the trajectories of the subjects in the NYX-2925 groups after early withdrawal are assumed to be worse than placebo by a fixed amount (δ). The value of δ is the adjustment added during imputation to the change from baseline NRS scores at each visit after study discontinuation. This increment is added only to the imputed change from baseline NRS scores at visits after study discontinuation of the subjects in NYX-2925. The value of δ will increase in increments of 0.5 (i.e., 1.0, 1.5, 2.0) up to the point at which the treatment difference at Week 12 is no longer statistically significant. This analysis provides a measure of the degree by which the subjects in the NYX-2925 groups who discontinued early would need to be worse (compared to those who did not discontinue) at each post-discontinuation visit in order for the null hypothesis of no treatment difference to no longer be rejected. Intercurrent events will be imputed by BLOCF as estimand in Section 6.11.1.1. Each imputed dataset produced through PROC MI procedure will be processed as follows:

- All values imputed for the placebo group will remain unchanged
- All values imputed for the NYX-2925 groups will be incremented by a value of δ , which will vary from 0 up to a value by which statistical significance is not reached
- The modified data will be analyzed using similar analysis as described in Section 6.11.2.

Results will then be combined using PROC MIANALYZE and will consequently be recorded

The “tipping point” is defined as the value of δ at which the result changes from a statistically significant treatment effect to a treatment effect that is no longer statistically significant. The larger the value of δ , the more robust the conclusion from the primary analysis with respect to assumptions around missing data.

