2.4.2 New Text

Section 6.11.3.1 Pattern-Mixture Model

To assess the robustness of the results to deviations from the MAR assumption in the primary analysis, a sensitivity analysis will be conducted such that non-monotone missing data will be imputed under a missing at random (MAR) assumption while the monotone missing data and data occurring after an ICE will be imputed under a missing not at random

(MNAR) assumption (i.e., that missingness is also dependent on the unobserved variable values).

2.5 Change 5

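### The control-based sensitivity analysis pools 20 imputations built on a single MCMC fill-in, so its p-value carries avoidable Monte Carlo noise; 200 draws in both steps would cut it about threefold

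*SAP*

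**What the plan says.** SAP 6.11.3.1 has two imputation steps. The first makes the missing pattern monotone by MCMC and produces one completed data set: "PROC MI DATA=DATAIN OUT=DATAIN_MONO SEED=373613962 NIMPUTE=1". The second imputes the monotone part from the placebo model: "PROC MI DATA= DATAIN_MONO SEED=373613962 NIMPUTE=20". The text gives the same number and seed: "PROC MI with options nimpute=20 and seed=373613962". The MMRM is fitted to each data set and the results are "combined across all 20 imputed datasets"; inference rests on "combined estimates using the standard multiple imputation technique via Rubin's" rules.

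Section 2.4.2 of the post-lock addendum widens what is imputed: "the monotone missing data and data occurring after an ICE will be imputed under a missing not at random". It leaves the number of imputations and the seed alone.

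For the tipping point, SAP 6.11.3.2 says "Each imputed dataset produced through PROC MI procedure will be processed as follows" and gives no number of imputations. It raises delta in steps of 0.5 until significance at Week 12 is lost.

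The level is set in SAP 6.11: "All statistical tests will be performed using a one-tailed 5% overall significance level as primary analysis". SAP 6.3.5 prints p-values to three decimals. The SAP gives no reason for 20, no Monte Carlo error and no run with a second seed.

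**The concern.** This analysis is the planned stress test of the missing-at-random assumption behind the primary result, and it is reported with p-values at the same 5% level. With few draws, the pooled estimate and the between-imputation variance both depend on the random numbers used. Near 0.05, readers may call the primary result supported or not supported because of the seed rather than the data. The tipping point is defined by a p-value crossing the threshold, so the same noise can move it to a neighbouring grid value. The single fill-in in the first step adds a smaller noise component that more draws in the second step cannot average away.

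**Working it through.** **Inputs from the documents.** 20 control-based draws and 1 MCMC draw (SAP 6.11.3.1); one-sided 0.05 (SAP 6.11); 85 analysed per arm, difference 0.73, SD 1.7, power about 88% (SAP 4).

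**Inputs assumed.** λ = B/T, the between-imputation share of total variance, taken as 0.05 to 0.3. The documents give no Week 12 missing rate; the 15% in SAP 4 is expected exclusion from the efficacy population, which is a different quantity.

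**1. The plan's own figure.** SE = 1.7 × √(2/85) = 0.261 and 0.73/0.261 = 2.80. One-sided power = Φ(2.80 − 1.645) = 0.876, which agrees with about 88%.

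**2. Noise from the second step.** With data held fixed, the pooled estimate varies over seeds with SD √(B/m). In z units SD(z) ≈ √(λ/m). If the p-value with unlimited draws is 0.05, the central 95% range over seeds is 1 − Φ(1.645 ± 1.96 × SD(z)).

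| λ (assumed) | SD(z), m = 20 | p range, m = 20 | SD(z), m = 200 | p range, m = 200 |
|---|---|---|---|---|
| 0.05 | 0.050 | 0.041–0.061 | 0.016 | 0.047–0.053 |
| 0.1 | 0.071 | 0.037–0.066 | 0.022 | 0.046–0.055 |
| 0.2 | 0.100 | 0.033–0.074 | 0.032 | 0.044–0.057 |
| 0.3 | 0.122 | 0.030–0.080 | 0.039 | 0.043–0.058 |

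**3. Check by simulation.** 85 per arm, 12 weeks, sequential placebo-based regression imputation, Week 12 ANCOVA standing in for the MMRM, Rubin pooling, and two assumed correlation patterns. The m = 20 ranges were:
- 15% dropout: λ about 0.13–0.16, p about 0.033–0.077.
- 25% dropout: λ about 0.20–0.23, p about 0.029–0.083.
- 35% dropout: λ about 0.24–0.28, p about 0.028–0.088.

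These are a little wider than the formula, which ignores the noise in B itself.

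**4. Noise from the first step.** At 25% dropout, SD(z) from the single fill-in was 0.021 and 0.026 with 3% of weeks missing intermittently (assumed), and 0.042 and 0.055 with 8%. That is about 0.02 to 0.05, against about 0.10 from the second step at m = 20.

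**5. Raising one step or both, at λ = 0.2.** Taking 0.05 for the first step:
- As planned: √(0.100² + 0.05²) = 0.112.
- 200 draws in the second step only: √(0.0316² + 0.05²) = 0.059, a factor of 1.9.
- 200 draws in both: √(0.0316² + 0.05²/200) = 0.032, a factor of 3.5.

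Taking 0.02 instead gives 0.102, 0.037 and 0.032, so factors of 2.7 and 3.2. Second-step noise alone falls by √(200/20) = 3.16.

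**6. How often two seeds would disagree.** The chance is about φ(d) × 1.128 × SD(z), where d is the distance of the expected z from 1.645. For SD(z) of 0.05 to 0.13, the span in a separate simulation at 100 per arm:
- Expected z at the threshold: 0.399 × 1.128 × SD(z) = 2% to 6%.
- Null: 0.6% to 1.5%.
- SAP design effect (z = 2.80): 1.2% to 3.0%, before any attenuation from control-based imputation.

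**The case against.** The strongest reply is that nothing here is invalid. Rubin's total variance, W + (1 + 1/m)B, already pays for finite m, and the price at λ = 0.3 is only 0.3/20 = 1.5% of the variance. That stands. The single fill-in is not represented in B, but its variance share is 0.02² to 0.05², or 0.04% to 0.25%; doubling it for the use of one draw gives at most 0.5%. A reader might infer that 20 draws make the test unsound; the SAP's pooling rule does not support that.

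A reader might also infer that the seed could be chosen to suit the result. It is fixed in SAP V1.0, and the addendum does not change it. The p-value is reproducible; what remains is arbitrariness near 0.05.

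The p ranges apply only if the p-value with unlimited draws sits at 0.05, and two-seed disagreement is uncommon even then. No decision rule hangs on this p-value, the primary MMRM uses no multiple imputation, and the tipping point runs only after a significant primary result. All of this stands and keeps the importance low.

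Finally, the sample code pools treatment differences by treatment without week. The figures above assume pooling by week. That is a separate matter which changing the number of imputations does not address.

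**Conclusion.** The point holds as a matter of precision. At 20 draws, a result whose limiting one-sided p is 0.05 would print within 0.041–0.061 if λ is 0.05 and within 0.030–0.080 if λ is 0.3. The size rests on the assumed λ; the order of magnitude agrees between formula and simulation. The effect on the tipping point is conditional: it needs the same 20 draws, which SAP 6.11.3.2 does not state, and a grid value near the threshold.

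Two stronger conclusions are tempting. One is that more draws remove the noise; at m = 200 the range still spans up to 0.043–0.058. The other is that editing the second `PROC MI` call is enough; the first-step noise of 0.02 to 0.05 would remain, as large as the whole second-step noise at m = 200 (0.016 to 0.039). Minor importance, free improvement.

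**What to change.** In SAP 6.11.3.1:
- Set `NIMPUTE=200` (or more) in the first call (MCMC, `IMPUTE=MONOTONE`), keeping the pre-specified seed.
- Sort the output by `_IMPUTATION_`, and run the second call with `BY _IMPUTATION_` and one draw per data set.
- Change the number 20 in the text, the code and the pooling sentence to match.

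In SAP 6.11.3.2, state that the tipping point uses the same number.

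The addendum was written after database lock and unblinding, so results may already exist. If they do, report the larger run beside the 20-draw run and label it as added.

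The cost is run time: 200 MMRM fits instead of 20, repeated for each delta in the tipping-point analysis. It needs no new data and has no effect on alpha.

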6.3.3 Validation Methods

All programming of datasets and outputs will be validated by independent programming (IP) of values, programmatic comparison and manual review of format compared to the SAP and agreed shell template. Figures will be validated by manual review of format and visual inspection of graphical display compared to tabulated data. Independent programming by a Statistician (Stat IP) will be performed for all analyses relating to the primary endpoint.

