6.3.6 Data Displays

All clinical data tabulations, figures and listings will be generated as individual Rich Text Format (.rtf) files using SAS (Version 9.4 or higher)¹. Data summaries, statistical analyses and graphical analyses will be reported within Section 14 of the CSR and individual subject data listings within [Appendix 16.2](#) of the CSR. Specifications (shells) for Tables, Figures and Listings will be provided as a separate document.

Subject disposition, baseline characteristics, demographic data, treatment exposure, compliance, medical history, concomitant medication, and adverse event data will be presented by treatment group and overall.

Other safety and efficacy data will be presented by treatment group only.

Treatment group labels will be displayed as follows:

NYX-2925 50 mg (N=XX)	NYX-2925 100 mg (N=XX)	Placebo (N=XX)
--------------------------	---------------------------	-------------------

Listings will be sorted in the following order: treatment group, subject, parameter, and visit unless otherwise stated. All data will be listed. For some listings, subjects who were not randomized will be presented but will be displayed after the randomized treatment groups

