6.11.2 Primary Efficacy Analysis

A one-tailed restricted maximum likelihood (REML)-based mixed model for repeated measures (MMRM) with one sided 95% CI will be utilized to assess the difference between treatment groups with respect to change from baseline to Week 12 in the weekly mean of the NRS score assessing average pain intensity in the past 24 hours.

The MMRM model will have site, treatment group, week, baseline NRS score, and treatment-by-week interaction as terms in the model. The unstructured covariance (UN) will be utilized as the within-subject covariance structure. In the event that the model fails to converge using the UN, the

Fisher scoring algorithm (via the SCORING option of the PROC MIXED statement) will be used to obtain the initial values of covariance parameters, otherwise, no-diagonal factor analytic structure (via the TYPE = FA0(T) option of the REPEATED statement) will be used as another option. When the above strategy fails, the successive univariate regression method will be applied. The Kenward-Roger degrees of freedom correction will also be used for this analysis.

The estimate of the difference between NYX-2925 50 mg versus placebo and NYX-2925 100 mg versus placebo at Week 12 and standard error (SE) will be derived from this model. Observed NRS scores at baseline and at each week, as well as their change from baseline at each week will be presented by treatment groups. The LS means, corresponding SEs, and 95% CI for each treatment group, the treatment difference of LS means, corresponding SEs, 1-sided 95% CI and 1-sided p-value at each week will be presented. The upper limit of the 95% CI of treatment difference will be extracted using ALPHA=0.10 statement for the bound in the unfavorable direction, and the limit in the favorable direction will be set to negative infinity.

The following is the sample SAS code that will be used for this analysis:

```
PROC MIXED DATA= DATAIN;
  CLASS USUBJID TREATMENT WEEK SITE;
  MODEL CHG = TREATMENT WEEK SITE TREATMENT*WEEK BASELINE / DDFM=KR;
  REPEATED WEEK / SUBJECT=USUBJID TYPE=UN;
  * extract two-sided 95%CI of LS MEANS each treatment groups by week;
  LSMEANS TREATMENT*WEEK / DIFF CL;
  * extract one-sided 95%CI of LS MEANS each treatment groups by week;
  LSMEANS TREATMENT*WEEK / DIFF CL ALPHA=0.10;
  RUN;
```

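### The printed code for the control-based imputation analysis pools treatment differences over weeks and comparators, so it cannot return the Week 12 dose-versus-placebo result

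*SAP*

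**What the plan says.** SAP 6.11.3.1 fits the primary MMRM to each of 20 imputed data sets, requests all pairwise differences of the treatment-by-week LS means, and pools them. The prose describes a step "where the treatment group LS means and their differences between treatments will be combined across all 20 imputed datasets", and the section closes by asking for results by week together with the treatment difference, its SE, one-sided interval and p-value.

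The differences are sorted with "PROC SORT DATA= DIFFS; BY TREATMENT" and pooled with "PROC MIANALYZE PARMS= DIFFS (WHERE=(WEEK=_WEEK", again with treatment as the only BY variable. In the step just before, the LS means are pooled by treatment and week.

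The quantity of interest is set elsewhere. SAP 6.11.1.1 names the Week 12 difference of each dose from placebo as the summary measure, and SAP 6.11.2 derives "The estimate of the difference between NYX-2925 50 mg versus placebo and NYX-2925 100 mg versus placebo at Week 12" from the model. Section 2.4.2 of the post-lock addendum rewrites the opening prose of 6.11.3.1 but prints no new code.

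**The concern.** Rubin's rules assume that the rows in a group are repeated estimates of one parameter that differ only through imputation. If week and comparator are left out of the grouping, differences between weeks and between comparators are averaged into the estimate and counted as between-imputation variance. The output is then neither a by-week result nor the Week 12 difference from placebo.

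SAP 6.11.3.1 presents this analysis as the stress test of the missing-at-random assumption behind the primary result. If it were run as printed, the verdict on robustness could depend on the time course of the effect and on how the treatment labels sort. Neither has anything to do with missing data.

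**Working it through.** **Row counts.** These need no assumption about the effect.

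- 3 treatments × 12 weeks = 36 cells, so 36 × 35 / 2 = 630 pairwise differences per imputation.
- The same-week filter leaves 3 pairs × 12 weeks = 36 rows per imputation, or 36 × 20 = 720 in all. It selects neither Week 12 nor placebo.
- Grouping by the first-named treatment gives one level with two comparators (2 × 12 × 20 = 480 rows) and one level with a single comparator (12 × 20 = 240 rows). The correct number is 20.
- If both LSMEANS statements (default and ALPHA=0.10) write to the same output table, the counts double. The estimates do not change, and the SEs below move by at most 0.0003.

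**Level order.** The code refers to treatment by a text value ("MODELOBS=(TREATMENT='Placebo"). SAP 6.3.6 lists labels under "Treatment group labels will be displayed as follows". If the variable carries those labels and they sort alphabetically, the order is 100 mg, 50 mg, placebo. The 100 mg group then mixes 100 mg versus 50 mg with 100 mg versus placebo, and the 50 mg group mixes weeks only. With 50 mg first, the two doses swap roles. With placebo first, the larger group mixes both doses and the other group is dose versus dose, so no group isolates one dose against placebo.

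**Planning figure.** SAP section 4 gives a difference of 0.73, SD 1.7, 85 per arm and one-sided 0.05.

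- SE = 1.7 × √(2/85) = 0.2608, so the within-imputation variance is W = 0.0680.
- 0.73 / 0.2608 = 2.80. Power = Φ(2.80 − 1.645) = 0.876, which agrees with the stated 88% or so.

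**Effect of the grouping.** Rubin's total variance is T = W + (1 + 1/m)B, where B is the variance over the m pooled rows. Assumptions: the same SE every week, no genuine between-imputation variance, equal effects of the two doses, and placebo as one of the two comparators in the larger group. Benefits are shown as positive numbers, and p-values are one-sided. The correct Week 12 result in all three rows is 0.73, SE 0.261, p 0.003.

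| Assumed time course | One comparator (m = 240) | Two comparators (m = 480) |
|---|---|---|
| Constant 0.73 | 0.73, SE 0.261, p 0.003 | 0.37, SE 0.449, p 0.21 |
| Full effect from Week 4: 0.73 × min(w/4, 1) | 0.64, SE 0.314, p 0.021 | 0.32, SE 0.431, p 0.23 |
| Linear: 0.73 × w/12 | 0.40, SE 0.335, p 0.12 | 0.20, SE 0.360, p 0.29 |

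Two cells written out:

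- Linear, one comparator: mean = 0.73 × 6.5/12 = 0.395. The spread over weeks is 0.73² × (143/12)/144 = 0.0441, so B = 0.0441 × 240/239 and T = 0.0680 + 0.0441 × 241/239 = 0.1125. SE = 0.335, t = 1.18.
- Constant, two comparators: half the rows are 0.73 and half are 0, so the mean is 0.365. T = 0.0680 + 0.365² × 481/479 = 0.2018. SE = 0.449, t = 0.81.

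**Opposite direction.** Suppose the effect is 0.73 through Week 5 and then falls by 0.073 a week to 0.73 × 0.3 = 0.219 at Week 12. The one-comparator group returns 0.73 × 9.2/12 = 0.56. The spread over weeks is 0.73² × (7.8/12 − (9.2/12)²) = 0.0332, so T = 0.0680 + 0.0332 × 241/239 = 0.101, SE 0.318, t 1.76, p about 0.04. The correct Week 12 result would be 0.219, t = 0.84, p about 0.20.

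**Genuine imputation variance.** Adding 5% to 20% of W leaves the means unchanged and raises the correct SE to between 0.268 and 0.287.

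**The case against.** The listing is labelled sample code, and the intent is clear from the prose. Pooling by treatment alone gives one row per level with no week, which cannot fill a by-week table, so a programmer would probably notice. The LS-means step also needs an edit: it is sorted with imputation as the first key ("PROC SORT DATA= LSMEANS; BY _IMPUTATION_ TREATMENT WEEK; RUN") but processed by treatment and week. SAP 6.3.3 provides independent programming, programmatic comparison and a check of format against the SAP and the agreed shells, and adds that "Independent programming by a Statistician (Stat IP) will be performed for all analyses relating to the primary endpoint". SAP section 11 assigns that level of validation to both tables concerned. The time courses above are assumptions, and which dose is mixed depends on level order. The primary MMRM is untouched.

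Most of this stands, and it lowers the chance that wrong numbers were reported. It does not remove the error. The SAP says the code will be used. Prose and code disagree, so a check against the SAP has no single standard, and the shells are not available to settle the matter. The row counts do not depend on the assumed time course, and no level order yields the Week 12 dose-versus-placebo difference.

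**Conclusion.** The point holds. The printed differences step pools 240 or 480 rows as if they were 20 imputations and does not estimate the quantity set in SAP 6.11.1.1 and 6.11.2, nor the by-week results that 6.11.3.1 itself asks for.

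The size depends on time course and level order. On the assumptions above, a true Week 12 effect of 0.73 is returned anywhere between 0.20 and 0.73. There is no error only for a constant effect in a single-comparator dose-versus-placebo group. A waning effect is overstated. If placebo sorts first and both doses have the same constant effect, the magnitude stays 0.73 but the sign is reversed.

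The documents do not show whether the reported tables came from this code. SAP 6.11.3.2 prints no pooling code for the tipping-point analysis, so its grouping can only be confirmed, not presumed wrong. This should be corrected, but it concerns a sensitivity analysis and leaves the primary result alone.

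**What to change.** 1. Confirm the grouping in the executed program, and state which code produced Tables 14.2.1.2.1 and 14.2.1.2.2.
2. Sort and pool the differences by TREATMENT, _TREATMENT and WEEK. Keep only NYX-2925-versus-placebo rows, align the sign if placebo sorts first, and keep one row per imputation (drop duplicates from the second LSMEANS statement). Report the Week 12 row as the key result.
3. Sort the LS means by TREATMENT and WEEK before pooling.
4. Confirm that the tipping-point runs use the same grouping.

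The cost is a few lines of code, and a re-run of two tables if they came from the printed listing. The addendum was written after database lock and unblinding, so any correction needs a dated note saying that it restores the pre-specified prose and does not change the method.
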